Product Use ¹¹			х				X												
Pod Weight Documentation ⁷							X												
Blood Sampling ¹²			Х				Х												
Urge to Smoke Assessments 13			Х				Х												

- ¹ Discharge from Test Visit 1 will be as follows. Day -1: Subjects in the continue-smoking arm who do not participate in the PK. Day 1: Subjects in the continue-smoking arm who participate in the PK assessment. Day 3: Subjects in the *my*bluTM arm who do not participate in the PK assessment. Day 5: Subjects in the *my*bluTM arm participating in the PK assessment.
- ² The clinic staff will make a telephone call within 24 48 hours prior to the scheduled visits to remind subjects of the date and time of the upcoming Test Visits.
- ³ Updated as necessary.
- ⁴ Study discharge/early termination events.
- ⁵ mybluTM arm only.
- ⁶ All subjects will smoke their usual brand combustible cigarettes prior to Day 1 and will use study product according to the randomization from Day 1 through discharge from the study.
- ⁷ Pods used during the 24-hour urine collections and PK sessions will be weighed prior to and following use.
- ⁸ Subjects will be trained on use of the ambulatory product use reporting system.
- ⁹ Collections for selected BoE, nicotine equivalents, and questionnaires for *my*bluTM subjects who participate in the PK sub-study.
- ¹⁰ Continue-smoking arm on Day 1, *my*bluTM arm on Day 5.
- ¹¹ Two product use sessions: fixed puffing regimen in the morning and an ad libitum regimen in the afternoon.
- ¹² Blood samples for nicotine concentration measurement will take place approximately 5 minutes prior to and at 3, 5, 7, 10, 12, 15, 20, 30, 60, 120 and 180 minutes following the start of each product use episode (Day 1 continue-smoking, Day 5 *my*bluTM).
- ¹³ Urge to smoke assessments will take place approximately 10 minutes prior to and within approximately 30 seconds prior to the scheduled blood draws at 5, 10, 15, 30, 60, and 120 minutes following the start of the *ad libitum* product use sessions.
- ¹⁴ At the discretion of the site, Test Visit 3 and Test Visit 5 may be ambulatory and subjects may complete selected procedures at home (e.g., 24-hour urine collection, completion of questionnaires). Subjects will be provided the materials required to complete the selected procedures and will be instructed on at-home procedures (e.g., urine collection method, questionnaires).

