Subjects randomized to the *my*bluTM arm will turn over all cigarettes to the clinic staff upon check-in on Day -2 and will smoke their usual brand cigarettes through 23:00 on Day -1. On the morning of Day 1, they will begin participation in a 3-day in-clinic product acclimation period through the evening of Day 3. The acclimation period will afford the subjects the opportunity to try each of the four *my*bluTM e-liquids in order to become accustomed to their use and to determine those that they would be willing to use during the study. Following product training on Day 1, subjects will use each of the four products individually for approximately 2 hours each, with the order of use selected by the subject. However, only one e-liquid may be used during each 2-hour period to ensure that subjects have an adequate time to try each. Following the last 2-hour period, subjects may choose any of the e-liquids freely through 23:00 on Day 2.

At 20:00 on Day 2, subjects will complete the mybluTM Product Preference Questionnaire (Appendix 2). Subjects will rank in the order of preference those products that they would be willing to use through the end of the study. It should be emphasized that they should only rank those products that they would be willing to use. Initial product assignment for each subject will be made by the clinic staff based on preference. Beginning on the morning of Day 3, subjects will use the assigned e-liquid through Day 28.

Subjects participating in the PK sub-study will continue to use the assigned product through the evening of Day 4. New pods will be issued for use during the 24-hour urine collection from the afternoon of Day 3 to Day 4. All pods used during the 24-hour urine collections will be weighed within 24 hours before and after use, with the weights documented. A new pod will be provided after completion of the urine collection.

Upon presentation to the clinic for Test Visits 3 and 5, subjects will turn over to the clinic staff the mybluTM device. Prior to the start of the urine collection, subjects may use the same pod as was being used prior to presenting to the clinic and new pods will be issued for use during the 24-hour urine collection. All pods used during the 24-hour urine collections will be weighed within 24 hours before and after use, with the weights documented. A new pod may be used after completion of the urine collection if time allows for product use prior to discharge from the test visit.

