#### 3. STUDY DESIGN

This will be an open-label, partially-randomized, parallel-arm, multi-site study in healthy adult smokers, consisting of two parts – the main study and a PK sub-study.

The main study will assess BoE, BoPH, physiologic effects, and subjective effects with use of *my*bluTM e-cigarettes relative to continuing to smoke combustible cigarettes. To account for potential attrition, up to 160 subjects are planned to be randomized into the *my*bluTM arm (with up to 40 subjects intended to be assigned to each *my*bluTM e-liquid) and up to 40 subjects will be randomized into the continuesmoking arm.

Baseline study assessments will be made during use of subjects' usual brand combustible cigarettes during the initial test visit through the morning of Day 1. All subjects in the *my*bluTM and continue-smoking arms will return to the clinic site for test visits scheduled to occur on Days 14, 28, 42, and 56 for post-baseline study assessments, compliance checks, and product dispensing and return. The subset of

subjects participating in the PK sub-study (described below) will also complete selected biomarker assessments (NNAL, NNN, 3-HPMA, CEMA, HMPMA, S-PMA, nicotine equivalents) on Days 3 and 4.

Subjects randomized to the *my*bluTM arm will participate in an in-clinic product acclimation period from Days 1 to 3. The acclimation period will afford the subjects the opportunity to try each of the four *my*bluTM e-liquids in order to become accustomed to their use and to determine those that they would be willing to use during the study. Initial product assignment for each subject will be based on preference as a method to enhance compliance. To further improve compliance through Day 56, at the end of Test Visit 3, subjects using a *my*bluTM product may be allowed to choose to switch to the alternate nicotine strength of their current flavor, to switch to the alternate flavor with the same nicotine strength as their initial choice, or to continue using the same e-liquid selected initially. This method for initial flavor assignment and the opportunity to re-select after 28 days of use is based on natural experimentation that consumers experience when choosing an e-cigarette flavor.

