#### 6. ANALYSIS OF STUDY ENDPOINTS

# 6.1 Product Use and Compliance

#### **6.1.1 Product Use and Compliance Assessments**

#### mybluTM Product Use

Following product training on Day 1, subjects will use each of the four test products individually for approximately 2 hours each, with the order of use selected by the subject. Following the last 2-hour period, subjects may choose any of the e-liquids freely through 23:00 on Day 2. At 20:00 on Day 2, subjects will complete the *my*bluTM Product Preference Questionnaire. Initial product assignment for each subject will be made by the study statistician or designee. Beginning on the morning of Day 3, subjects will use the assigned e-liquid through Day 28 and will be given the opportunity at Visit 3 to switch to the alternate nicotine strength of their current flavor, to switch to the alternate flavor with the same nicotine strength as their initial choice, or to continue using the same e-liquid selected initially through Day 57 (Visit 5, last study day). Each day from Day 3 through discharge from the study on Day 57, subjects randomized to the *my*bluTM arm will self report their product use via a text message system (Medquest).

Subjects participating in the PK sub-study will continue to use the assigned product through the evening of Day 4. All pods used during the 24-hour urine collections will be weighed within 24 hours before and after use, with the weights documented. On Test Visit 3 (Day 28) and Test Visit 5 (Day 56) as well, all pods used during the 24-hour urine collections will be weighed within 24 hours before and after use, with the weights documented.

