#### 7.4 Adverse Events

All adverse events (AEs) occurring during this clinical trial will be coded using the Medical Dictionary for Regulatory Activities (MedDRA®), Version 21.0.

All AEs captured in the database will be listed in by-subject data listings including verbatim term, coded term, product, severity, relationship to study product, and action; however, only product use-emergent AEs (PUEAEs) will be summarized.

A PUEAE is defined as an AE that is starting or worsening at the time of or after the first randomized study product use. Each PUEAE will be attributed to a study product based on the onset date and time of the AE.

If the onset time of an AE is missing and the onset date is the same as the first study product use date, then the AE will be considered product use emergent in the study product. If onset time of an AE is missing and the onset date does not fall on a study product use date, then the AE will be considered product use emergent for the last study product administered. If the onset date of an AE is missing, then the AE will be considered product use emergent, unless the onset date is known to have occurred within or between specific product use days.

PUEAEs will be tabulated by System Organ Class (SOC) and Preferred Term. Summary tables will include number of subjects reporting the AE and as percent of number of subjects used study product by product. The number of AEs will be tabulated in a similar manner. Tables which tabulate the number of PUEAEs by severity and relationship to study product will also be included.

In addition, adverse events occurred during baseline period on Day -2 and day -1 will be summarized separately.

Serious adverse events (SAEs), if present, will also be listed. Applicable narratives will be included in the CSR.

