# 7.7 Electrocardiogram

A single 12-lead electrocardiogram (ECG) will be recorded at Screening for all product arms. For *my*bluTM and continue-smoking arms, the ECG will also be performed at the discharge from the study (Day 57) or upon early termination. For JUUL arm, the ECG will be performed at Day 1 and upon early termination.

Descriptive statistics will be reported for ECG parameters by product arm and time point. Unscheduled events or rechecks post randomization will not be included in summaries. Similarly early termination results will not be included in summaries.

ECG results will be listed by subject.

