#### Product Trial# Adverse Event\* Number of Subjects Who Received Study Product XX(100%) XX(100%) XX(100%) XX(100%) XX(100%) XX(100%) XX(100%) XX(100%) XX(100%) Number of Subjects With Adverse Events X(X%) X(X%)Eve disorders $X(X_8)$ $X(X_8)$ $X(X_8)$ $X(X_8)$ $X(X_8)$ $X(X_8)$ Vision blurred $X(X_8)$ $X(X_8)$ $X(X_8)$ $X(X_8)$ $X(X_8) X(X_8)$ Gastrointestinal disorders $X(X^8)$ $X(X^8)$ $X(X^8)$ $X(X^8)$ $X(X^8)$ $X(X^8)$ $X(X_8)$ $X(X_8)$ X(X%)X(X%)X( Dyspepsia X%) X ( X%) X ( X%) X ( X%) $X(X_8) X(X_8)$ Nausea $X(X_8)$ $X(X_8)$ $X(X_8)$ $X(X_8)$ $X(X_8)$ $X(X_8)$ $X(X_8) X(X_8)$ Musculoskeletal and connective tissue $X(X\%) \times (X\%) \times (X\%) \times (X\%) \times (X\%) \times (X\%)$ $X(X_8)$ $X(X_8)$ disorders Back pain X(X%) $X(X_8)$ $X(X_8)$ $X(X_8)$ $X(X_8)$ X%) $X(X_8)$ $X(X_8)$ X(X%)X( X%) X(X%) X(X%)X( $X(X_8) X(X_8)$ Muscle cramps Musculoskeletal pain $X(X^{\circ})$ $X(X^{\circ})$ $X(X^{\circ})$ $X(X^{\circ})$ $X(X^{\circ})$ $X(X^{\circ})$ X(X) X(X) $X(X_8)$ $X(X_8)$ $X(X_8)$ $X(X_8)$ $X(X_8)$ Nervous system disorders $X(X_8)$ $X(X_8)$ Headache NOS $X(X_8)X(X_8)$ X%) X(X%) X(X%) X(X%) $X(X_8) X(X_8)$ Χ( X%) Reproductive system and breast disorders X(X%) X(X%) X(X%) X(X%) X(X%) X(X%) $X(X_8)$ $X(X_8)$ Vaginal discharge $X(X_8)$ $X(X_8)$ $X(X_8)$ $X(X_8)$ $X(X_8)$ $X(X_8)$ $X(X_8)$

Note: \* Adverse events are classified according to MedDRA Version 21.0.

Product X: < >

Program: /CAXXXX/sas\_prg/stsas/tab cdash\_tblae1a\_auto.sas DDMMMYYYY HH:MM

# Only include the adverse events occurred during the product trial period.

^ Adverse events occurred during the product trial period are excluded from Overall summary.

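### The planned AE tables leave product-trial events out of Overall and never count each myblu subject once, and the post-use ECG and spirometry rows cover only subjects who reached Day 57 (minor)

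*SAP*

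**What the plan says.** **Adverse events.** SAP 7.4 states: "A PUEAE is defined as an AE that is starting or worsening at the time of or after the first randomized study product use". Footnote 6 to protocol Table 2 says that after baseline all subjects "will use study product according to the randomization from Day 1 through discharge from the study". The protocol's Definition of Terms makes randomization the assignment to an arm, not to an e-liquid. First randomized use in the myblu arm is therefore Day 1, when the four e-liquids are first tried. SAP 7.4 continues: "Each PUEAE will be attributed to a study product based on the onset date and time of the AE".

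The AE shells in SAP 10.2 have entries for Product Trial, Products A to F, and Overall (clearest in the Table 14.3.1.2 shell). Product Trial holds only trial-period events. Of the Overall entry, the footnote to all three shells says: "Adverse events occurred during the product trial period are excluded from Overall summary". The only other AE table in the SAP Section 14 list is the SAE table.

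**ECG and spirometry.** For the myblu and continue-smoking arms, SAP 7.7 says that after screening "the ECG will also be performed at the discharge from the study (Day 57) or upon early termination". SAP 7.11 gives the same timing for spirometry. Both sections then keep early-termination results out of the summaries. SAP 7 has all case report form data listed by subject, early termination included.

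**The concern.** Secondary objective 10 is to confirm the safety of myblu e-cigarettes over 56 days. A reader would expect one figure for it: the proportion of myblu subjects with at least one AE from first use to the end of the study. No planned table gives that figure. The nearest candidate, Overall, omits events from the days of first exposure and mixes in two products that are not myblu.

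The ECG and spirometry rule raises a similar issue. AEs are among the reasons for discontinuation in protocol 4.4, so those who leave early may differ from those who stay. A post-use row confined to Day 57 attenders describes the subjects who stayed.

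**Working it through.** **1. Denominators.** Protocol 3.1 plans up to 175 myblu and 40 continue-smoking subjects, and 20 JUUL subjects. 175 + 40 + 20 = 235, which reproduces the planned total in the synopsis. (SAP 3 still gives up to 160 for myblu; the current protocol figure is used here.) The myblu share of Overall is 175/235 = 74.5%.

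**2. Can the myblu figure be rebuilt from the columns?** No. With attribution by onset time, one subject can count under Product Trial and again under an assigned e-liquid, or under two e-liquids after the switch allowed at the end of Test Visit 3. The SAP does not say outright whether columns A to D also exclude trial-period events, but on either reading the subject counts overlap and cannot be added.

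**3. How wide is the gap?** Let *t* be the proportion of myblu subjects with a trial-period AE and *l* the proportion with a later one. The proportion with any AE satisfies

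max(*t*, *l*) ≤ any AE ≤ min(1, *t* + *l*),

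and equals *l* + (1 − *l*)*t* if the two are independent. The rates below are illustrative assumptions. The only AE frequency in the documents is in protocol 1.2: 4 of 15 subjects (27%) in a short six-period crossover that included cigarettes and another device, which does not carry over to this design. Take *l* = 40% (0.40 × 175 = 70 subjects), with no subject in two of A to D:

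| *t* | Full overlap | No overlap | Independent | Largest addition to Overall |
|---|---|---|---|---|
| 5% | 70 (40%) | 78.75 (45%) | 75.25 (43%) | 8.75/235 = 3.7 points |
| 10% | 70 (40%) | 87.5 (50%) | 80.5 (46%) | 17.5/235 = 7.4 points |
| 20% | 70 (40%) | 105 (60%) | 91 (52%) | 35/235 = 14.9 points |

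The smallest addition to Overall is zero (full overlap). Restoring the events can only leave Overall incidence unchanged or raise it.

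**4. ECG and spirometry.** The timings in SAP 7.7 and 7.11 leave two kinds of post-use value in the main-study arms: Day 57 and early termination. The exclusion removes the second, so the post-use row contains Day 57 values only. Screening rows still include everyone.

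The number omitted cannot be derived. The one related figure is the over-enrolment in protocol 4.5 and 7.1, with 29 completers wanted at Day 28 in each of five cohorts: (175 + 40) − 5 × 29 = 70 of 215 (32.6%). By arm this is 175 − 4 × 29 = 59 of 175 myblu (33.7%) and 40 − 29 = 11 of 40 continue-smoking (27.5%).

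**The case against.** The best defence is that nothing is hidden. Trial-period AEs have their own column and a plain footnote, and separating them is sensible because four e-liquids are tried before one is assigned. Table 14.3.1.1 has a row for subjects with any AE under each product. The study hypothesis is tested separately for each e-liquid, and no document promises a pooled myblu figure. SAP 10 says the shells show general layout and may change. On ECG and spirometry, early-termination values come from mixed exposure times and should not be merged with Day 57. Under protocol 4.4 they are obtained only where feasible and where the investigator judges them necessary. An abnormal finding in an early leaver can still be recorded as an AE (protocol 6.9).

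Most of this stands, and it is why the point is minor. It does not answer objective 10, which concerns myblu e-cigarettes over the whole 56 days. Nor does it answer SAP 7.7 and 7.11, which are body text rather than shells.

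Two stronger readings are tempting:

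- **Day 3 events have no home.** The protocol describes "participation in a 3-day in-clinic product acclimation period through the evening of Day 3", while SAP 6.1.1 says "Beginning on the morning of Day 3, subjects will use the assigned e-liquid through Day 28". But free choice among the e-liquids ends at 23:00 on Day 2, and AEs are attributed by onset time, so a Day 3 event falls naturally to the assigned product. A definition would remove doubt; the passages do not force two answers.
- **The protocol and SAP conflict on early-termination spirometry**, because the Day 57 spirometry entry in protocol Table 2 lacks the early-termination footnote. The table as read from the PDF has visibly lost cells, and protocol 4.4 calls for the discharge safety procedures in early leavers, which agrees with SAP 7.11.

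**Conclusion.** The point holds as a minor reporting gap. Overall excludes events that the SAP itself classes as product-use-emergent, it is not a myblu figure, and no planned column counts each myblu subject once. The post-use ECG and spirometry rows in the main-study arms describe only those who reached Day 57.

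Its size is unknown. The AE ranges rest entirely on assumed rates; what does not depend on them is the direction, since including the trial-period events cannot lower Overall incidence.

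A reader might infer that the plan gives no AE incidence for myblu at all, or that first-exposure events are suppressed. The documents do not support this: incidence is planned for each e-liquid and for the trial period, and every AE is listed. A reader might also infer that about a third of subjects will be missing from the Day 57 rows. The 70 of 215 is an over-enrolment allowance against a Day 28 target. It assumes exactly 29 completers in each cohort although e-liquids are assigned by preference, and it ignores the replacements allowed by protocol 4.6. It is not a forecast of loss by Day 57.

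**What to change.** - Keep the Product Trial column, delete the footnote that excludes its events from Overall, and include them there.
- Add a column such as 'Any myblu, Day 1 to end', counting each subject once.
- Define the product trial period in SAP 7.4 by study day and time, for example from first use on Day 1 until use of the assigned e-liquid starts on the morning of Day 3.
- In the ECG and spirometry summaries keep the Day 57 row and add a separate early-termination row with its own n. Add a note that these tests are done only where feasible and judged necessary, so that the row is a selected subset.

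The cost is some SAP wording, one AE column and one row in each of two tables, all from data already collected. The downside is a little more table work and an Overall AE incidence that stays the same or rises.

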### Clinical Study Report No. CA22747

Page 1 of X

Table 14.3.1.2 Product Use-emergent Adverse Event Frequency by Study Product - Number of Adverse Events (% of Total Adverse Events) (Safety Population)

Adverse Event*	Produ Tria			А		В	(	C		D	Ε	2	Ε	Ţ.	Over	call^
Number of Adverse Events	XX (2	L00%)	XX (1	L00%)	XX (1	L00%)	XX (1	L00%)	XX (1	100%)	XX (1	L00%)	XX (1	L00%)	XX (1	L00%)
Eye disorders	X (	X%)	X (	X%)	X (	X%)	X (	 X%)	X (	X%)	X (	X%)	Х(	X%)	Х (	 X%)
Vision blurred	Х (	X%)	Х (	X%)	Х (	X%)	Х (	X%)	Х (	X%)	Х (	X%)	Х (	X%)	Х (	X%)
Gastrointestinal disorders	Х (	X%)	Х (	X%)	Х (	X%)	Х (	X%)	Х (	X%)	Х (	X%)	Х (	X%)	Х (	X%)
Dyspepsia	Х (	X%)	Х (	X%)	Х (	X%)	Х (	X%)	Х (	X%)	Х (	X%)	Х (	X%)	Х (	X%)
Nausea	Х (	X%)	Х (	X%)	Х (	X%)	Х (	X%)	Х (	X%)	Х (	X%)	Х (	X%)	Х (	X%)
Musculoskeletal and connective tissue	Х (	X%)	Х (	X%)	Х (	X%)	Х (	X%)	Х (	X%)	Х (	X%)	Х (	X%)	Х (	X%)
disorders																
Back pain	Х (	X%)	Х (	X%)	Х (	X%)	Х (	X%)	Х (	X%)	Х (	X%)	Х (	X%)	Х (	X%)
Muscle cramps	Х (	X%)	Х (	X%)	Х (	X%)	Х (	X%)	Х (	X%)	Х (	X%)	Х (	X%)	Х (	X%)
Musculoskeletal pain	Х (	X%)	Х (	X%)	Х (	X%)	Х (	X%)	Х (	X%)	Х (	X%)	Х (	X%)	Х (	X%)
Nervous system disorders	Х (	X%)	Х (	X%)	Х (	X%)	Х (	X%)	Х (	X%)	Х (	X%)	Х (	X%)	Х (	X%)
Headache NOS	Х (	X%)	Х (	X%)	Х (	X%)	Х (	X%)	Х (	X%)	Х (	X%)	Х (	X%)	Х (	X%)
Reproductive system and breast disorders	Х (	X%)	Х (	X%)	Х (	X%)	Х (	X%)	Х (	X%)	Х (	X%)	Х (	X%)	Х (	X%)
Vaginal discharge	Х (	X%)	Х (	X%)	Х (	X%)	Х (	X%)	Х (	X%)	Х (	X%)	X (	X%)	Х (	X%)

Note: \* Adverse events are classified according to MedDRA Version 21.0.

Product X: < >

Program: /CAXXXXX/sas\_prg/stsas/tab cdash\_tblae2a\_auto.sas DDMMMYYYYY HH:MM

# Only include the adverse events occurred during the product trial period.

^ Adverse events occurred during the product trial period are excluded from Overall summary.

#### Clinical Study Report No. CA22747

Page 1 of X

Table 14.3.1.3 Adverse Event Frequency by Study Product, Intensity, and Relationship to Study Product
- Number of Subjects Reporting Events (Safety Population)

	044	Number of		Intens	sity	Relationship to Study Product			
Adverse Event*	Study Product 	Subjects with Adverse Events	Mild M	oderate	Severe	Unrelated	Possibly	Probably	
Abdominal pain	X	X	X	X	X	X	X	X	
Constipation	X	X	X	X	X	X	X	X	
Dry throat	X	X	X	X	X	X	X	X	
Headache	X	X	X	X	X	X	X	X	
	X	X	X	X	X	X	X	X	
Product Trial#		X	X	X	X	X	X	X	
Study Product A		X	X	X	X	X	X	X	
Study Product B		X	X	X	X	X	X	X	
Study Product C		X	X	X	X	X	X	X	
Study Product D		X	X	X	X	X	X	X	
Study Product E		X	X	X	X	X	X	X	
Study Product F		X	X	X	X	X	X	X	
Overall^		X	X	X	X	X	X	X	

Note: \* Adverse events are classified according to MedDRA Version 21.0.

When a subject experienced the same AE at more than one level of intensity during a product use period, only the most severe one was counted.

When a subject experienced the same AE at more than one level of product relationship during a product use period, only the one most closely related to study product was counted.

Product X: < >

Program: /CAXXXXX/sas prg/stsas/tab cdash tblae3a auto.sas DDMMMYYYY HH:MM

# Only include the adverse events occurred during the product trial period.

^ Adverse events occurred during the product trial period are excluded from Overall summary.

Clinical Study Report No. CA22747

Table 14.3.2.1 Serious Adverse Events

Page 1 of X

There were no serious adverse events recorded during the study

Program: /CAXXXXX/sas\_prg/stsas/tab cdash\_tblae\_ser.sas DDMMMYYYY HH:MM

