6.9.2 Reporting

Events reported prior to use of study products on Day -2 will be documented as baseline signs and symptoms in the medical history. All events occurring after use of study products on Day -2 must be recorded on the eCRF as AEs. Documentation will include the date and time of onset, action taken, outcome (resolved, improved, unchanged, worse, fatal, or unknown/lost to follow-up), duration, relationship to product administration, and severity for each event. AEs will be coded using most current version of the Medical Dictionary for Regulatory Activities (MedDRA)[®] available at

The Investigator will review each event and assess its relationship to product administration as unrelated, unlikely, possibly, probably, or likely.

In addition, each sign or symptom reported will be graded on a 3-point severity scale using mild, moderate, or severe.

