7.6 Safety

All clinical safety data will be listed by subject and time point and summarized as described in the SAP.

All reported events captured in the database will be listed in by-subject data listings. However, only study product use-emergent AEs. A study product use-emergent AE is defined as an AE that is starting or worsening at the time of or after the first study product use on Day -2.

Frequencies of subjects with study product use-emergent AEs, regardless of relationship to study product will be summarized and sorted by system organ class. Frequencies of subjects

with study product use-emergent SAEs will be likewise summarized. Frequencies of study product use-emergent AEs will be summarized by severity and relationship to study product.

Changes in physical examinations (if any) will be described in the text of the final report.

All prior and concomitant medications recorded during the study will be listed by subject.

The following pre- and post-bronchodilator lung function variables will be summarized.

- Measured and percent of predicted FEV₁
- Measured and percent of predicted FVC
- Measured and percent of predicted FEV₁:FVC ratio
- Measured and percent of predicted FEF_{25-75%}

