## 10. TABLE AND FIGURE SHELLS

Appendix 16.2.8.5 Appendix 16.2.8.6

The following table shells provide a framework for the display of data from this study. The shells may change due to unforeseen circumstances. These shells may not be reflective of every aspect of this study, but are intended to show the general layout of the tables that will be presented and included in the final report. Unless otherwise

FeNO Measurement (Safety Population)

Spirometry (Safety Population)

[figure not shown]
Nerudia Ltd.
nyblu E-cigarettes
Clinical Study Report No. CA22747

noted, all tables will be presented in Times New Roman font size 8. These tables will be generated off of the ADaM Version 1.0.

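### The SAP's only adverse-event table by relationship to product has three relationship columns for the protocol's five grades, with no rule for placing 'unlikely' or 'likely'.

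*SAP*

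**What the plan says.** Under Protocol 6.9.2 (Reporting), the investigator is to "assess its relationship to product administration as unrelated, unlikely, possibly, probably, or likely". That is five grades. The same section has severity "graded on a 3-point severity scale using mild, moderate, or severe".

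Protocol 7.6 (Safety) fixes what must be summarised: "Frequencies of study product use-emergent AEs will be summarized by severity and relationship to study product". SAP 7.4 (Adverse Events) repeats the commitment: "Tables which tabulate the number of PUEAEs by severity and relationship to study product will also be included". Neither section names the relationship categories to be shown or provides for merging any of them.

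The layout is in SAP 10.2, in the shell for Table 14.3.1.3. Under the relationship heading the columns read "Unrelated Possibly Probably". The footnote handles a subject who has the same event at more than one relationship level within a product use period: "only the one most closely related to study product was counted".

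SAP 8 declares no departure from the protocol's analyses.

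**The concern.** A relationship table should have a place for every grade the investigator can assign. Here two grades have none. One of them, 'likely', comes last in what reads as an ascending list and so appears to be the firmest attribution to product. The footnote sharpens the problem, because it tells the programmer to take the most closely related level, and when that level is 'likely' there is no column to put it in.

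Secondary objective 10 is to confirm the safety of the test e-cigarettes over the 56-day use period. The list of outputs in SAP 9 (section 14.3.1) has three adverse-event summary tables, and only Table 14.3.1.3 covers relationship. If it is programmed as drawn, the count of events attributed to product will be incomplete, or will depend on a merging choice that nobody wrote down.

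**Working it through.** The plan states no figure to reproduce. The check is a count of categories against columns, followed by a look at what the gap does to the table.

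**1. Is the three-column layout real, or was a column lost when the PDF was read?** Each event row in the shell has eight entries after the event term: product (1) + number of subjects (1) + intensity (3) + relationship (3) = 8. Each product total row has seven, which is the same without the product entry. Header and rows agree in width, so the layout is as the authors drew it.

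**2. Grades against columns.**

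| Scale | Grades in Protocol 6.9.2 | Columns in the Table 14.3.1.3 shell | Grades without a column |
|---|---|---|---|
| Severity | 3 | 3 | 0 |
| Relationship | 5 | 3 | 2 (unlikely, likely) |

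Severity is complete, so the mismatch is confined to relationship.

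**3. Is there a mapping elsewhere?** Protocol 7.6 and SAP 7.4 name no categories and give no rule for combining them. SAP 8 declares no change. The shell carries no programmer note on relationship, although other shells do carry notes where adaptation was expected, for instance on which study days and products to show, or which columns to delete in a parallel design.

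**4. Effect on the table.** For one event and one product, let U, N, P, R and L be the numbers of subjects whose most related grade is unrelated, unlikely, possibly, probably and likely, each subject counted once.

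- Subjects with the event: U + N + P + R + L.
- Sum of the three columns if the other two grades are left out: U + P + R.
- Shortfall: N + L.

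If the programmer merges instead, taking adjacent columns only, 'unlikely' can be omitted, put under Unrelated or put under Possibly (3 options), and 'likely' can be omitted or put under Probably (2 options). That gives 3 × 2 = 6 different tables from the same data. The total in the two columns above Unrelated runs from P + R to N + P + R + L, a spread of N + L.

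**5. Would five columns sum to the subject total?** Not necessarily under the present footnote. It applies to the same event within a product use period, and the protocol's Definition of Terms sets two such periods for the main-study arms. Take a subject who stays on one product and has the same event graded possibly in Period 1 and likely in Period 2. Read literally, the footnote allows that subject to count in two relationship columns (1 + 1 = 2) but only once in the subject column. The intensity footnote is limited to a product use period in the same way.

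**The case against.** The strongest reply is that this is a layout template. SAP 10 says so: "These shells may not be reflective of every aspect of this study, but are intended to show the general layout of the tables". The block is visibly generic, with placeholder event terms, and the serious-event table is pre-filled with a statement that none occurred. The operative text in Protocol 7.6 and SAP 7.4 asks for a summary by relationship and excludes no grade. This stands, and it makes the matter a correctable inconsistency in a shell, not a decision to drop grades. But the caveat supplies neither the missing grades nor a mapping, so someone still has to settle the point before the table is produced.

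A second reply is that the events remain visible. This also stands. A subject graded 'likely' or 'unlikely' still counts in the table's subject column and intensity columns, and in Tables 14.3.1.1 and 14.3.1.2. SAP 7.4 has every event "listed in by-subject data listings including verbatim term, coded term, product, severity, relationship to study product, and action", and the shell for Appendix 16.2.7.1.2 has a relationship column. A reader might infer from the shell that the events most firmly attributed to product disappear from the safety report; the documents do not support that. What goes missing is their attribution in the summary. A listing does not replace it, because Protocol 7.6 asks for frequencies.

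Third, the ranking of 'likely' above 'probably' is inferred from list order; Protocol 6.9.2 defines none of the grades. The inference is reasonable but should be labelled as one.

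Fourth, the only relationship data in the documents come from the earlier single-use study of the same system (Protocol 1.2). Of its 10 events, one was graded possibly related and nine unlikely or unrelated. It was too small and too short to predict 56 days of use. It does show 'unlikely' being used, so that omission may matter in practice as much as the omission of 'likely'.

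**Conclusion.** The mismatch holds. Two of the five protocol grades, 'unlikely' and 'likely', have no column and no mapping in the only planned summary of adverse events by relationship. A programmer following the shell must either leave N + L subjects out of the relationship columns for a given event and product, or merge them by an unwritten rule.

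The size cannot be taken further. A reader might want to state what share of related events would be missing, but nothing in either document supports a figure for how often 'likely' or 'unlikely' will be the most related grade. The table is descriptive, and no hypothesis test depends on it.

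The conclusion rests on the shell being followed as drawn. The description of 'likely' as the strongest grade rests on the order of the protocol's list.

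**What to change.** Give the Table 14.3.1.3 shell five relationship columns in protocol order: Unrelated, Unlikely, Possibly, Probably, Likely. Alternatively, keep three columns and state in SAP 7.4 and in the table footnote how all five grades map to them.

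If a check is added that the relationship columns sum to the number of subjects with the event, reword the footnote so that each subject is counted once per event and product row, at the most related grade across both product use periods. The intensity footnote needs the same change if its columns are to be checked in that way.

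A derived column combining the related grades is optional. Neither document asks for one, and adding it would require the SAP to define which grades count as related.

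The cost is two more columns, or one sentence of mapping, plus the footnote edit if the check is adopted. Protocol 6.9.2 already requires relationship to be recorded on the eCRF for each event, so nothing new is collected.
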